6.2.4 Outcome Models for Primary Endpoint

The primary endpoint, time to medical treatment failure, will be investigated by plotting Kaplan-Meier survival curves for the original unweighted samples. Superimposed on this survival plot (e.g. with dashed lines) will be adjusted Kaplan-Meier curves for the two groups that incorporate the IPTW balancing weights. Therefore, the dashed lines will represent the survival curves after balancing the larotrectinib and external cohort databases. Median and first and third quartile estimates of survival will be reported using Kaplan-Meier method for both original unweighted and weighted samples. 95% confidence intervals will also be reported. In addition, duration of follow-up will be calculated using the Kaplan-Meier method after reversing *censoring* and *event* status.

```
proc lifetest data=temp outsurv=temp2;
  time osdur*oscnsr(1);
  strata trt;
  weight wgt;
RUN;
```

Example code for incorporating the IPTW weights is shown above. Here, the SAS routine `proc lifetest` calculates confidence intervals for quartiles by applying the formula given by Xie and Liu[7] for the variance of the adjusted Kaplan-Meier estimator.

Statistical tables will report the log-rank test, comparing larotrectinib and comparator groups. Per Xie and Liu[7], an analogous log-rank test for the weighted sample will also be computed. This adjusted log-rank test is available within `proc lifetest` by specifying that the `weight` statement should contain IPTW weights, e.g. `weight wgt`.

Additionally, a hazard ratio will be computed using a weighted Cox Proportional Hazards model, regressing survival time on an indicator variable denoting treatment status (larotrectinib/comparator) and incorporating the IPTW weights. To construct the confidence interval of the hazard ratio, the bootstrap-based variance estimator will provide approximately correct estimates of standard errors as it takes into account the fact that the IPTW weights are only estimates from the available data. For each of bootstrap samples (e.g. 200 samples) drawn from the data, weights will be drawn from the PS model and the log-hazard ratio will be calculated from the weighted Cox model. The standard deviation of the estimated log-hazard ratios (i.e., the estimated regression coefficient for the treatment status indicator) across the 200 bootstrap samples will be used as the bootstrap estimate of the standard error of the estimated regression coefficient obtained in the original data set. Ninety-five percent confidence intervals of the hazard ratio can be constructed as:

$$\exp [\hat{\beta} \mp 1.96 \times \text{SE}(\hat{\beta})]$$

where $\hat{\beta}$ denotes the estimated treatment effect in the original weighted sample, and $\text{SE}(\hat{\beta})$ denotes the estimated standard error of the treatment effect using bootstrapping.

Hazard ratios will also be reported for the unweighted samples.

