9.7.4 Outcome model

Time-to-event variables

The primary endpoint, time to medical treatment failure, and other time-to-event endpoints detailed above will be investigated by plotting Kaplan-Meier survival curves for the original unweighted samples. Superimposed on these survival plots (e.g. with dashed lines) will be adjusted Kaplan-Meier

curves for the two groups that incorporate the IPTW balancing weights. Therefore, the dashed lines will represent the survival curves after balancing the larotrectinib and external cohort databases. Median estimates of survival and survival probabilities at meaningful timepoints determined by the data, e.g. 6 and 12 months, will be displayed using Kaplan-Meier method for both original unweighted and weighted samples. 95% confidence intervals will also be reported.

Statistical tables will report the log-rank test, comparing larotrectinib and comparator groups. Per Xie and Liu, an analogous log-rank test for the weighted sample will also be computed. Additionally, a hazard ratio will be computed using a weighted Cox Proportional Hazards model, regressing survival time on an indicator variable denoting treatment status (larotrectinib/comparator) and incorporating the IPTW weights. To construct the confidence interval of the hazard ratio, the bootstrap-based variance estimator will provide approximately correct estimates of standard errors as it takes into account the fact that the IPTW weights are only estimates from the available data. For each of bootstrap samples (e.g. 200 samples) drawn from the data, weights will be drawn from the propensity score model and the log-hazard ratio will be calculated from the weighted Cox model. The standard deviation of the estimated log-hazard ratios (i.e., the estimated regression coefficient for the treatment status indicator) across the 200 bootstrap samples will be used as the bootstrap estimate of the standard error of the estimated regression coefficient obtained in the original data set. Ninety-five percent confidence intervals of the hazard ratio can be constructed as:

$$\hat{\beta} \mp 1.96 \times \text{SE}(\hat{\beta})$$

where $\hat{\beta}$ denotes the estimated treatment effect in the original weighted sample, and $\text{SE}(\hat{\beta})$ denotes the estimated standard error of the treatment effect using bootstrapping.

Hazard ratios will also be reported for the unweighted samples.

Response variables

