As of the 20 July 2021 cut-off, there are 49 SCOUT IFS patients available for analysis. The pooled external cohorts from Curie and CWS will comprise N=42. Therefore, the power calculations in the protocol can be updated with current information on sample size as follows:

- N=49 IFS patients for SCOUT
- N=42 for pooled external control cohorts
- pE=0.04 (probability of failure in SCOUT) and pC=0.19 (probability of failure in control) per protocol assumptions
- Optimistic scenario of a strong treatment effect (HR=0.25)
- Power=51%
- Power cannot exceed 62.9% for N=49 for SCOUT and an unlimited number of subjects in the external arm

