4.1 General Principles

The statistical evaluation will be performed by using the software package SAS version 9.4 (SAS Institute Inc., Cary, NC, USA) for all outputs assigned for publication, or R (version 4.1.0 [2021-05-18]) or higher for exploratory analysis.

The creation of TLFs will follow the standard as described in RD-SOP-1215.

Descriptive analysis of the data will be performed using summary statistics for categorical and quantitative (continuous) data. Continuous data will be described by the number of non-missing values, median, mean, standard deviation, minimum, and maximum as well as lower and upper quartiles. Frequency tables will be generated for categorical data.

Time-to-event analyses, and other model-based analyses, will be described in detail in subsequent sections.

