6.3 Analysis of Secondary and Exploratory Variable(s)

The following time-to-event secondary endpoints, [sections 6.3.1](#) to [6.3.8](#), will be analyzed using the steps outlined above, and incorporating the IPTW weights calculated for the primary endpoint. The sensitivity analyses detailed in [section 6.2.5](#) will be limited to the primary endpoint.

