6.7 Additional Analyses Planned to be Reported Outside the Study Report

Not applicable.

7. Document History and Changes in the Planned Statistical Analysis

The complementary analysis on patients with IFS or other STS with *NTRK* gene fusion will no longer take place as there is only one STS patient in the Curie Database and none in the CWS. In its place, analyses will be performed on the population of patients with IFS having documented *NTRK* gene fusion.

The protocol described a sensitivity analysis on choice of index date of the primary endpoint, for subjects in either arm who are treated with a second line or more of systemic therapy or larotrectinib. The index date was specified as the start of second line in both groups. However, as shown below in 2, fewer control subjects received a second line than anticipated, and a larger number of subjects in SCOUT took larotrectinib as the secondline therapy. Therefore, the analysis would have had an unbalanced sample size at N=32 versus 8. In addition, 14 of the 32 larotrectinib subjects start at line 3 to 6, leading to a conservative analysis that unduly favors the control group.

In order to provide a more balanced analysis, we propose to replace this sensitivity analysis for the choice of index date with the sensitivity analysis based on exact matching on the line of therapies, approach as detailed in Section 6.2.5. A subgroup analysis was planned in those treated with second line of treatment in both groups. A similar subgroup analysis will be conducted when comparing first line Larotrectinib patients versus external controls taking at least 1 line of therapy, which was added to Section 6.2.5.

Table2 Line of Therapy

	Larotrectinib	Control
1st Line	19 (37%)	34 (81%)
2nd Line or Higher	32 (63%)	8 (19%)

8. References

- [1] Rosner B. (2006). *Fundamentals of Biostatistics*. (6-th edition). Thomson Brooks/Cole.

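### The standard error of the primary hazard ratio is the SD of bootstrap log-hazard ratios, some of which are not finite at the SAP's own event rates

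*SAP*

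**What the plan says.** SAP 6.2.4 reports Kaplan-Meier curves and log-rank tests, unweighted and weighted, and adds a hazard ratio from a weighted Cox model with treatment as the only regressor. For its confidence interval, bootstrap samples are drawn (200 is given as an example), the propensity weights are obtained again in each, and the weighted Cox model is refitted. The standard deviation of the log-hazard ratios "across the 200 bootstrap samples will be used as the bootstrap estimate of the standard error of the estimated regression coefficient". The interval is the exponential of the estimate plus or minus 1.96 times that value. The SAP describes this estimator as approximately correct. Protocol 9.7.4 has the same procedure.

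The updated power calculation in SAP section 4 uses 49 SCOUT patients and 42 external controls, with "pE=0.04 (probability of failure in SCOUT) and pC=0.19 (probability of failure in control) per protocol assumptions", and a hazard ratio of 0.25.

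SAP 6.3 states that the secondary time-to-event endpoints "will be analyzed using the steps outlined above, and incorporating the IPTW weights calculated for the primary endpoint".

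The available text does not say what to do when a resample, or the original data, has no event in one group. SAP 6.2.5 deals with extreme propensity scores and large weights, and SAP 4.3 with missing data. The end of the SAP, including the appendix in its contents list, was not available.

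**The concern.** In a Cox model with one binary regressor, if a group has no event the partial likelihood keeps rising as the log-hazard ratio goes to minus (or plus) infinity. Software returns whatever value it had reached when its convergence criterion was met. Weighting does not help, because IPTW rescales events and cannot create them.

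A standard deviation taken over all resamples is then partly a property of the stopping rule. Two analysts who follow SAP 6.2.4 faithfully on the same data could report very different intervals. A third who discards the divergent fits would report a narrow one. The weighted hazard ratio is the adjusted effect estimate of a comparison meant to inform a reimbursement reassessment (Protocol 7.6), so the choice should not be made after the data are seen.

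**Working it through.** **Reproducing the plan's figure.** The SAP's formula is Φ(√(k·m)·|IRR−1|/(k·IRR+1) − 1.96), with k = 49/42 = 1.167 and m = 49×0.04 + 42×0.19 = 1.96 + 7.98 = 9.94. This gives √(1.167×9.94) = 3.405; 3.405×0.75/1.292 = 1.977; Φ(0.017) = 50.7%. The SAP states 51%. With unlimited controls k·m tends to 49×0.19 = 9.31 and the power is 62.9%, as stated. The inputs are therefore read correctly.

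**Larotrectinib events in the original data.**
- At pE = 0.04: 1.96 expected. P(0) = 0.96^49 = 13.5%; P(1) = 27.6%; P(2) = 27.6%; P(≤2) = 68.8%.
- At HR 0.25 with pC = 0.19: pE = 1 − 0.81^0.25 = 0.0513, so 2.51 expected. P(0) = 7.6%; P(1) = 20.1%; P(2) = 26.0%; P(≤2) = 53.7%.
- At HR 0.5 with pC = 0.19: pE = 0.10, so 4.9 expected. P(≤2) = 12.0%.

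**Share of resamples with no larotrectinib event, given d observed.** The SAP does not say whether resampling is pooled or within cohort. The formulas are (1−d/91)^91 and (1−d/49)^49.

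| d | pooled | within cohort | pooled, of 200 |
|---|---|---|---|
| 1 | 36.6% | 36.4% | 73 |
| 2 | 13.2% | 13.0% | 26 |
| 3 | 4.7% | 4.5% | 9 |
| 4 | 1.7% | 1.5% | 3 |
| 5 | 0.6% | 0.5% | 1 |

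At least one empty resample in 200 is practically certain up to d = 3. The chance is 69% at d = 5 and 4.5% at d = 8. SAP section 7, Table 2 lists 19 + 32 = 51 larotrectinib patients rather than 49; using 51 leaves the pooled share at d = 2 at 13.2%. With 8 control events, a resample without a control event is negligible (0.02%).

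**Effect on the standard error.** These figures come from simulation and rest on assumptions outside the documents: exponential event times, complete or staggered follow-up, two covariates with stabilised weights refitted in each resample, and assumed stopping values for the log-hazard ratio. SAS was not run. The table shows median standard errors.

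| d | kept, stop at −10 | kept, stop at −20 | dropped | √(1/d + 1/8) |
|---|---|---|---|---|
| 1 | 3.93–3.95 | 8.75–8.76 | 0.61–0.63 | 1.06 |
| 2 | 2.92–2.96 | 6.25–6.35 | 0.71 | 0.79 |
| 3 | 2.00–2.03 | 4.08–4.11 | 0.71–0.73 | 0.68 |

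The last column is a rough count-based benchmark that ignores weighting. A separate unweighted run at d = 2 gave 2.95–3.01 kept at −10 and 0.67–0.69 dropped. In one unweighted data set with 2 larotrectinib and 8 control events, a tight criterion gave 9.0, a loose one 3.5, and dropping gave 0.96. The dependence on the stop is thus clear, while the exact values are only illustrative. When empty resamples were dropped, the Wald interval at 1 event covered the true hazard ratio in 70–86% of data sets.

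**The case against.** **The planning rates may be too low.** SAP section 7, Table 2 shows 8 of 42 controls (19%) at second line or higher. Under SAP 6.2.1 the control index date is the start of first-line chemotherapy and any later systemic therapy is a failure. That component alone therefore reaches pC = 0.19, which makes 0.19 a floor. At HR 0.25, assumed pC values of 0.25, 0.30 and 0.35 give 3.4, 4.2 and 5.0 larotrectinib events, and P(≤2) falls to 33%, 20% and 11%. P(0) = (1−pC)^(49×0.25) falls to 2.9%, 1.3% and 0.5%. This stands: the problem may be smaller than the planning inputs suggest.

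**A careful analyst would notice.** At 2 events the simulated median interval is 0.0006 to 62–68 if divergent fits are kept at −10, and 0.05 to 0.79–0.83 if they are dropped. The first is visibly not a converged result. That is true, but the remedy would then be chosen with the results in view.

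**Dropping is nearly harmless.** From 3 events the simulated standard error is not short, and at 2 it is only slightly so. This also stands. The clear shortfall is at 1 event, which has a probability of 28% at pE = 0.04 and 20% at HR 0.25.

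**The analysis is exploratory.** The protocol says so, SAP section 4 sets no formal hypothesis, and the hazard ratio comes in addition to Kaplan-Meier estimates and log-rank tests, which need no finite hazard ratio. This limits the consequence but does not make the stated interval well defined.

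**Conclusion.** The point holds as a defect in the rule for the interval. Applied literally at the SAP's own inputs, SAP 6.2.4 takes a standard deviation over values of which about 37%, 13% or 5% are not finite when 1, 2 or 3 larotrectinib events are observed. These shares, and the 13.5% or 7.6% chance that the hazard ratio itself is not finite, follow from the SAP's figures by arithmetic. The standard errors rest on the simulation assumptions listed above.

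A reader might infer that the handling of empty resamples decides whether the study shows an effect. In the simulation at 2 events the interval excluded 1 in 62–66% of data sets with such fits dropped, and in none with them kept at −10. The documents do not support that conclusion. The contrast needs divergent fits to be kept at an invented stopping value, the log-rank tests are untouched, and actual event counts may exceed the planning values. By about 5 events the problem has largely faded.

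Nor can one say that the sponsor has no rule at all, since the end of the SAP was not available. It can be said only that none appears in the methods sections.

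**What to change.** Amend SAP 6.2.4 before the analysis:

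1. Replace the SD-based Wald interval with bootstrap percentile limits. Resample within cohort, re-estimate the weights each time and use more replicates, for example 2,000.
2. Count a resample without a larotrectinib event as log-HR = minus infinity, and report how many there were. The lower limit is then 0 whenever they exceed 2.5% of resamples, as expected at 1 to 3 observed events (36.4%, 13.0% and 4.5% within cohort).
3. If the original data contain no larotrectinib event, report the hazard ratio as not estimable and rely on the log-rank test and the Kaplan-Meier estimates.
4. State in SAP 6.3 that the same rule holds for the secondary time-to-event endpoints, worded for an empty group on either side. Protocol 7.8 quotes 2.9% radiotherapy, 6.9% mutilating surgery and 5.2% death from disease under conventional treatment. In 42 controls that would be about 1.2, 2.9 and 2.2 events (illustrative, since that population differs).

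In an unweighted simulation at the SAP's inputs, such percentile limits covered the true hazard ratio in 97–98% of data sets with at least one larotrectinib event, against 91–96% for dropping empty resamples. Coverage with re-estimated weights was not checked.

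A Firth-penalised weighted Cox model may be added as a sensitivity analysis. It should not replace the main estimate: it raised the hazard ratio towards 1 by 41–44% at 1 event and 18–20% at 2. Its simulated coverage of 96–97% was no better than that of the percentile limits.

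The cost is SAP wording, modest programming and slightly more computing, with no new data. With few events the interval may have a lower limit of 0, which reflects how little the data say about that side.

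### The hazard-ratio confidence interval should rest on a stated, larger number of bootstrap resamples with a fixed seed: the only count given is 200, which leaves avoidable simulation noise of roughly 12% to 17% either way in the upper limit

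*SAP*

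**What the plan says.** SAP 6.2.4 fits a weighted Cox model and obtains the standard error of the log-hazard ratio by bootstrap: "For each of bootstrap samples (e.g. 200 samples) drawn from the data, weights will be drawn from the PS model". The SD of the resulting log-hazard ratios "across the 200 bootstrap samples will be used as the bootstrap estimate of the standard error", and the 95% limits are the exponentials of the estimate minus and plus 1.96 standard errors. Protocol 9.7.4 describes the same bootstrap: "For each of bootstrap samples (e.g. 200 samples) drawn from the data, weights will be drawn from the propensity score model".

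The number 200 is thus first an example and then, two sentences later, simply the number. Neither bootstrap description gives a seed, a tolerance for simulation error, or a rule for resamples in which the model cannot be fitted.

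SAP 6.3 carries the method to the other time-to-event endpoints, which "will be analyzed using the steps outlined above, and incorporating the IPTW weights calculated for the primary endpoint".

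**The concern.** The bootstrap standard error is itself an estimate from a finite number of random draws, so the same data analysed with another seed give another interval. With about ten expected events the standard error is large on the log scale. A small relative error in it is multiplied by 1.96 and exponentiated, so it shows in the reported limit. Sampling error cannot be avoided with 49 and 42 patients; this additional noise can. The interval is the main statement of uncertainty about the primary hazard ratio in a comparison requested for the reimbursement reassessment, and its readers will look at its width.

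**Working it through.** **Inputs.** From SAP section 4 (Sample Size and Power Considerations): 49 patients on larotrectinib and 42 controls; failure probabilities, given as "pE=0.04 (probability of failure in SCOUT) and pC=0.19 (probability of failure in control) per protocol assumptions"; hazard ratio 0.25; two-sided alpha 0.05. From SAP 6.2.4: 200 resamples and a Wald interval. The documents give no standard error for the log-hazard ratio, so a range is derived below.

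**1. The plan's own power.** Expected events are 49 × 0.04 + 42 × 0.19 = 1.96 + 7.98 = 9.94, and k = 49/42 = 1.167. The SAP formula gives √(1.167 × 9.94) × 0.75 / (1.167 × 0.25 + 1) = 1.977, and Φ(1.977 − 1.96) = 50.7%, which matches the stated 51%. With unlimited controls, Φ(√(49 × 0.19) × 0.75 − 1.96) = 62.9%, also as stated.

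**2. Range for the standard error (assumption).**
- Implied by the plan's power, reading 1.977 as the expected z: ln 4 / 1.977 = 0.70.
- Schoenfeld approximation: 1/√(9.94 × 49 × 42 / 91²) = 0.64.
- Inverse-event approximation: √(1/1.96 + 1/7.98) = 0.80.

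None of these allows for the effect of weighting.

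**3. Monte Carlo error of the SD.** The relative error is 1/√(2(B − 1)). This is 5.0% for B = 200 and 1.6% for B = 2000. From the chi-square distribution of a sample variance, the 95% range of the SD over seeds is a factor of 0.902 to 1.098 for B = 200 and 0.969 to 1.031 for B = 2000.

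**4. Effect on the upper limit.** A factor f on the standard error multiplies the upper limit by exp(1.96 × SE × (f − 1)). At hazard ratio 0.25:

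| SE | Upper limit | 95% seed range, B = 200 | Change | 95% seed range, B = 2000 | Change |
|---|---|---|---|---|---|
| 0.64 | 0.88 | 0.78 to 0.99 | −12% to +13% | 0.84 to 0.91 | ±4% |
| 0.70 | 0.99 | 0.86 to 1.13 | −13% to +14% | 0.94 to 1.03 | ±4% |
| 0.80 | 1.20 | 1.03 to 1.40 | −14% to +17% | 1.14 to 1.26 | ±5% |

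The end-to-end ratio of the seed range is 1.28 to 1.36 with 200 resamples and 1.08 to 1.10 with 2000. At SE 0.70 the SD of the log upper limit over seeds is 1.96 × 0.70 × 0.050 = 0.069, or about 7%.

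**5. How often two seeds disagree about 1.** For a dataset with observed z, the chance that a seed gives an interval excluding 1 is p(z) = P(χ² on B − 1 df < (B − 1)(z/1.96)²). Two independent seeds disagree with probability 2p(1 − p). Averaged over z ~ N(1.98, 1), the optimistic scenario, this is 4.4% for B = 200 and 1.4% for B = 2000. At hazard ratio 1 it is 1.3% for B = 200.

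**6. Simulation of the planned procedure.** The simulation used 49 v 42 patients, stabilized weights re-estimated in each resample and a weighted Cox model. It assumed exponential event times and three normal covariates, and capped divergent log-hazard ratios at 20. There were 300 datasets per scenario.
- *Non-estimable resamples dropped:* the end-to-end ratio with 200 resamples is 1.33 to 1.37. Two seeds disagree in 3% to 5% of datasets near hazard ratio 0.25 and 1.5% at hazard ratio 1. This agrees with steps 4 and 5.
- *All resamples kept:* near hazard ratio 0.25 the median standard error is about 5 to 6, and the interval excludes 1 in under 1% of datasets.

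The reason is arithmetic. With 2 larotrectinib events among 91 patients, a resample contains neither with probability (89/91)^91 = 13.2%, and the log-hazard ratio then diverges. The chance that the data themselves contain no larotrectinib event is 0.96^49 = 13.5%.

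**The case against.** The count is given as an example, so the team may run more without amending anything. The protocol synopsis calls the results exploratory, and both documents set no formal hypothesis, so nothing turns on whether the interval excludes 1. The unweighted and weighted log-rank tests in SAP 6.2.4 do not use the bootstrap. Protocol 9.8 keeps the datasets and programs for audit, so a seed set in the code would be recoverable.

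Most of this is fair, and it limits what can be claimed. Two stronger statements are tempting. A reader might infer that the upper limit moves by about 30% with the seed. That is the full width of the 95% seed range; a typical move is about 7%. A reader might also infer that the seed settles the reading in about one dataset in six. About 15% of datasets do fall in a band where at least 2.5% of seeds give the minority answer. But two seeds actually disagree in about 4%, and only near a hazard ratio that the SAP calls optimistic. At SE 0.64 or 0.80 the seed range around an estimate of 0.25 does not cross 1 at all.

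The noise also cannot be treated apart from resamples without events. The figures above need those resamples to be dropped, and the SAP has no such rule. If all are kept, divergent resamples dominate the SD, and more resamples do not cure that.

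What stands: 200 is the only number in either document, a programmer following the text would run it, and no seed is stated.

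**Conclusion.** The point holds as a matter of precision and reproducibility. With 200 resamples the upper limit of the primary hazard ratio carries seed noise with a 95% range of about −12% to +17% across standard errors of 0.64 to 0.80. With 2000 this falls to about ±4% to 5%. The same applies to the time-to-event endpoints in SAP 6.3, by an amount that depends on their own standard errors.

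The documents do not support the reading that the seed would change the study's conclusion, because they attach no decision to excluding 1. The figures rest on standard errors derived from the SAP's planning inputs, and on a near-normal bootstrap distribution or the removal of non-estimable resamples. With about 2 expected larotrectinib events, the handling of those resamples matters more to the interval than their number.

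**What to change.** In SAP 6.2.4, replace both mentions of 200 with a fixed number of at least 2000 resamples, and state the seed. A seed alone makes the interval reproducible but no more precise, so both are needed. Because SAP 6.3 refers back to these steps, the change carries to the time-to-event endpoints there without further text.

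As a companion edit, state how resamples with a non-estimable hazard ratio are handled, and report how many there were for each endpoint.

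The cost is a few minutes of computing and a few words in the SAP. There is no statistical downside.
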